7.1.2 Analysis

The following analysis periods will be considered for all AE tables:

- DB treatment daily PE period
- DB treatment post-daily PE period
- OL treatment daily PE period
- OL treatment post-daily PE period
- Overall treatment period
- FU period
- Overall study period

Summaries on AEs will be presented by treatment group (Caplacizumab, Placebo, OL Caplacizumab, Caplacizumab Total) and by analysis period. The 'Caplacizumab Total' group will combine events that have occurred for all caplacizumab-treated subjects. For subjects who received placebo in the DB treatment period, only events after switch to open-label caplacizumab will be counted for the Caplacizumab Total group.

A general summary table will be presented by treatment group and analysis period, reporting the number and percentage of subjects, the number of events and the incidence per 100 patient months, which will be calculated as: $100 \times (\text{Number of subjects with AE}) / (\text{Total number of months observed within analysis period, summed for all subjects})$. The following categories will be included in the summary table:

- Subjects with at least one TEAE
- Subjects with at least one serious TEAE
- Subjects with at least one TEAE leading to death
- Subjects with at least one TEAE for which the study drug was interrupted
- Subjects with at least one TEAE for which the study drug was withdrawn
- Subjects with at least one TEAE that was considered at least possibly treatment-related by the investigator
- Subjects with at least one serious TEAE that was considered at least possibly treatment-related by the investigator
- Subjects with at least one bleeding event, i.e. an event documented as event indicating an increased bleeding tendency
- Subject with at least one bleeding event, based on the Standardized MedDRA Query (SMQ) 'Haemorrhage terms (excluding laboratory terms)'
- Subjects with at least one thromboembolic event, based on the SMQ 'Embolic and thrombotic events (arterial, venous, and vessel type unspecified and mixed arterial and venous)'
- Subjects with at least one hypersensitivity reaction, based on the SMQs 'Hypersensitivity' (Narrow), 'Anaphylactic reaction' (Narrow) and 'Angioedema' (Narrow)
- Subjects with at least one hypersensitivity reaction, based on the SMQs 'Hypersensitivity' (Narrow), 'Anaphylactic reaction' (Narrow) and 'Angioedema' (Narrow), considered at least possibly treatment-related by the investigator.

TEAEs, serious TEAEs, non-serious TEAEs and clinically significant TTP and bleeding events will be summarized for each treatment group (Caplacizumab, Placebo, OL Caplacizumab, Caplacizumab Total) by system organ class and preferred term. This will be done for each analysis period. The number of events and the number and percentage of subjects having an event will be presented.

TEAEs and serious TEAEs will be summarized for each treatment group (Caplacizumab, Placebo, OL Caplacizumab, Caplacizumab Total) by system organ class, preferred term and severity. This will be done for each analysis period. The number of events and the number and percentage of subjects having an event will be presented for the worst severity reported for each event (within the same analysis period – see also Section 7.1.1). This analysis will be repeated for the bleeding events.

TEAEs considered at least possibly treatment-related by the investigator and serious TEAEs considered at least possibly treatment-related by the investigator will be summarized for each treatment group (Caplacizumab, Placebo, OL Caplacizumab, Caplacizumab Total) by system organ class and preferred term. This will be done for each analysis period. The number of events and the number and percentage of subjects having an event will be presented. This analysis will be repeated for the bleeding events.

TEAEs leading to study drug withdrawal and TEAEs leading to study drug interruption will be summarized separately and combined for each treatment group (Caplacizumab, Placebo, OL Caplacizumab, Caplacizumab Total) by system organ class and preferred term. This will be done for each analysis period. The number of events and the number and percentage of subjects having an event will be presented.

Treatment-emergent thromboembolic events, based on the SMQ ‘Emolic and thrombotic events (arterial, venous, and vessel type unspecified and mixed arterial and venous)’, will be summarized for each treatment group (Caplacizumab, Placebo, OL Caplacizumab, Caplacizumab Total) by system organ class and preferred term. This will be done for each analysis period. The number of events and the number and percentage of subjects having an event will be presented.

[figure not shown]
Hypersensitivity reactions (including anaphylaxis and angioedema) will be summarized for each treatment group (Caplacizumab, Placebo, OL Caplacizumab, Caplacizumab Total) by system organ class and preferred term. This will be done for each analysis period. The number of events and the number and percentage of subjects having an event will be presented. This analysis will be repeated for hypersensitivity reactions considered at least possibly treatment-related by the investigator.

The tables by system organ class and preferred term are sorted by decreasing frequency of system organ class and preferred term overall.

All recorded adverse events will be listed.

A detailed list of tables and listings can be found in Section 14.6 and Section 16.6 respectively.

7.1.3 *Exploratory analysis*

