Results from the caplacizumab arm suggest that ADAMTS13 activity data could identify subjects who were at risk for early relapse. In 7 of 8 subjects with a relapse in the first month, it occurred within 4-10 days after stopping caplacizumab. All 7 subjects had ADAMTS13 activity values <10% at baseline, during and near the end of the treatment period, indicating unresolved underlying disease activity. In the 8th subject, the relapse event occurred at 30 days after stopping caplacizumab treatment. This subject had normalization of ADAMTS13 activity during and near the end of the treatment period. However at the time of the relapse, ADAMTS13 activity was again suppressed <10%, which suggests a *de novo* TTP event. Conversely, 22 caplacizumab-treated subjects did not have an exacerbation or relapse, with ADAMTS13 activity data available near the end of the treatment period for 16/22 patients. In 13 of 16 subjects without exacerbation or relapse, ADAMTS13 activity had returned to values \geq 10% near the end of the treatment. ADAMTS13 activity results from the placebo treated subjects supported the potential predictive value of the marker: for 14 of 16 placebo subjects without exacerbation or relapse (ADAMTS13 data available for 16/23 placebo subjects), ADAMTS13 activity values were \geq 10% near the end of the placebo treatment period. A total of 11 placebo subjects had an exacerbation during the treatment period, and ADAMTS13 activity data were available for 8 of them. Seven of 8 placebo subjects with an exacerbation had ADAMTS13 activity <10% around the time of the exacerbation, while the 8th subject had a borderline ADAMTS13 activity value of 11%. In summary, the data support ADAMTS13 activity as a potential marker to identify patients at risk for exacerbation or relapse, specifically patients with signs of ongoing active disease during the treatment period who are at risk of relapse early after stopping caplacizumab treatment.

No significant unanticipated safety concerns were raised for treatment with caplacizumab in this study. The results were as expected for the population of patients with acquired TTP. The overall duration of exposure to study drug was similar in the two treatment arms.

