4.3.6 Presentation of treatment groups

The following treatment group labels will be used in the tables, listings and figures, unless specified otherwise:

- Caplacizumab
- Placebo
- Open-label (OL) Caplacizumab

Treatment groups Caplacizumab and Placebo refer to the initial treatment group prior to a potential switch to open-label caplacizumab, and only data up to the switch are used in the analyses of these treatment groups. The OL Caplacizumab treatment group will only be used for analyses after the switch to open-label caplacizumab.

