7.1 Adverse Events

7.1.1 Methods and definitions

All adverse events will be coded using the latest version of the Medical Dictionary for Regulatory Activities (MedDRA).

All adverse events starting or worsening in severity (for pre-existing conditions) from the start of study drug administration until completion of the subject's last visit are considered treatment-emergent adverse events (TEAE).

Adverse events will be placed into analysis periods (phases, periods and subperiods) according to their start date(time). The AE will only be presented in the analysis period during which it started, i.e. period start date(time) \leq AE start date(time) \leq period stop date(time). There will be no imputation of other missing date(time) fields, nor of the missing parts of other partially known date(time) fields. When needed (e.g., an incomplete date(time) leads to a double phase allocation), the following rules will be applied: adverse events will be allocated on all analysis levels (i.e., for analysis phases, periods and subperiods, see Section 4.4) according to their start date(time). In case the adverse event (AE) start date(time) is incomplete, the allocation will be done according to the available parts of the AE start date(time) and taking into account the AE end date(time) (i.e., the AE start date(time) cannot be later than the AE end date(time)):

- When, due to missing date(part) an allocation needs to be made to an analysis phase, the AE will be allocated to the treatment phase and not the screening or follow-up phase (worst-case allocation).
- When an allocation needs to be made within the treatment phase to an analysis period, the AE will be allocated to the double-blind treatment period.
- When an allocation needs to be made within an analysis period, the event will be allocated to the daily PE subperiod.

CONFIDENTIAL

If the AE start date is completely missing but AE end date and study drug administration are non-missing and AE end date is before the first study drug administration and after signing ICF, then the AE is defined as pre-treatment. All adverse events emerging during the screening period will only be listed and will not be presented in any of the tables. These events are not TEAEs. All tables will thus present TEAEs only.

According to ICH-E3, the drug relatedness as assessed by the investigator will be dichotomized as follows:

- Drug-related: at least possibly drug-related, OR with a missing drug-relatedness (= worst-case).

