- Not drug-related: less than possibly drug-related.

In tabulations this dichotomized drug-relatedness will be used, but in the listings the original drug-relatedness will be presented.

Relationship to PE and relationship to corticosteroids are collected as related or not related. Missing relatedness will be considered as related.

When cross-tabulating AE preferred terms versus an AE attribute (e.g., severity), the worst-case is always applied within each analysis period. This means that when a subject has the same AE preferred term twice in the same analysis period, then the subject is reported only once: with the worst severity. If this happens in two different analysis periods, the subject is reported twice: once in each analysis period.

AE onset day and AE duration are defined as follows:

- AE onset day
 - = AE start date – date of first study drug intake + 1 day (when the AE start date is completely known)
 - = missing (when the AE start date is incomplete or unknown).
- AE duration
 - = AE stop date – AE start date + 1 day (when both dates are completely known)
 - = trial termination date – AE start date + 1 day (when the AE start date is fully known but the AE is not resolved at the end of the trial): in this case the duration will be presented as “>x days” in the listing rather than “x days”
 - = missing (when the AE start date is incomplete or unknown, or when the AE has resolved but with an incomplete or unknown end date).

These derived parameters will only be presented in the listings. Note that the start and stop times of the AE are not used.

All percentages will be calculated against the total number of subjects (within each treatment group) that are still in the study in that particular analysis period.

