14 INDEX OF TABLES

14.1 General

Table 14.1.1.1: Subject disposition: Tabulation by analysis population

Tabulation of the number of subjects in each of the analysis populations defined in Section 4.1.
Population: all screened population.

Table 14.1.1.2: Subject disposition: Tabulation by country and site

Tabulation of the number of subjects per country and site.
Population: ITT population.

Table 14.1.1.3: Subject disposition: Tabulation by time point

Tabulation of the number of subjects per time point.
Population: ITT population.

Table 14.1.1.4: Subject disposition: First and last contact in the trial

Tabulation of the following 3 dates:

- Date of the first signature on trial ICF or pre-trial ICF
- Last visit date (all visits; including unscheduled visits)
- Last date of contact in the study with any subject (i.e., the last DM.RFENDTC).

Population: all screened population.

Table 14.1.1.5: Subject disposition: Descriptive statistics of the analysis period duration (days)

Descriptive statistics of the analysis period duration. The duration (days) is derived as follows: period end date – period start date + 1. This table will represent phases, periods and subperiods.

Population: ITT population.

Table 14.1.1.6: Trial termination: Tabulation

Tabulation of completion/discontinuations and the reasons for discontinuation.

Population: ITT population.

Table 14.1.1.7: Major protocol deviations: Tabulation

Tabulation of the major protocol deviations per category (DVDECOD) (see Section 5.2 for more details).

Population: ITT population.

Table 14.1.2.1: Demographic data: Tabulation and descriptive statistics

Continuous parameters: descriptive statistics.

Categorical parameters: frequency tabulation.

Population: ITT population.

Table 14.1.2.2: Baseline disease characteristics: Tabulation and descriptive statistics

Continuous parameters: descriptive statistics.

Categorical parameters: frequency tabulation.

Population: ITT population.

Table 14.1.2.3: Concomitant immunosuppressive therapies

Tabulation of type of immunosuppressive therapies (corticosteroid / rituximab / other immunosuppressive).

Population: ITT population.

Table 14.1.2.4: Concomitant immunosuppressive therapies by generic term

Tabulation of the generic terms of immunosuppressive therapies.

Population: ITT population.

Table 14.1.2.5: Concomitant non-immunosuppressive therapies by generic term

Tabulation of the generic terms of non-immunosuppressive therapies.

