14.6 Safety: Adverse Events

Table 14.3.1.1: Treatment-emergent adverse events: Summary table

Tabulation of the number and percentage of subjects, the number of events and the incidence per 100 patient months for the following:

- Subjects with at least one TEAE
- Subjects with at least one serious TEAE
- Subjects with at least one TEAE leading to death
- Subjects with at least one TEAE for which the study drug was interrupted
- Subjects with at least one TEAE for which the study drug was withdrawn
- Subjects with at least one TEAE that was considered at least possibly treatment-related by the investigator
- Subjects with at least one serious TEAE that was considered at least possibly treatment-related by the investigator
- Subjects with at least one bleeding event (i.e. event documented as event indicating an increased bleeding tendency)
- Subjects with at least one bleeding event, based on SMQ 'Haemorrhage terms (excluding laboratory terms)'
- Subjects with at least one hypersensitivity reaction, based on the SMQs 'Hypersensitivity' (Narrow), 'Anaphylactic reaction' (Narrow) and 'Angioedema' (Narrow)
- Subjects with at least one hypersensitivity reaction, based on the SMQs 'Hypersensitivity' (Narrow), 'Anaphylactic reaction' (Narrow) and 'Angioedema' (Narrow), considered at least possibly treatment-related by the investigator

Population: safety population.

Table 14.3.1.2: Treatment-emergent adverse events: Tabulation of all adverse events

Tabulation of TEAE preferred terms per system organ class.

Population: safety population.

Table 14.3.1.3: Treatment-emergent adverse events: Tabulation of all adverse events by severity

Tabulation of TEAE preferred terms per system organ class by severity.

Population: safety population.

Table 14.3.1.4: Treatment-emergent adverse events: Tabulation of serious adverse events

Tabulation of serious TEAE preferred terms per system organ class.

Population: safety population.

Table 14.3.1.5: Treatment-emergent adverse events: Tabulation of serious adverse events by severity

Tabulation of serious TEAE preferred terms per system organ class by severity.

Population: safety population.

Table 14.3.1.6: Treatment-emergent adverse events: Tabulation of non-serious adverse events

Tabulation of non-serious TEAE preferred terms per system organ class.

Population: safety population.

Table 14.3.1.7: Treatment-emergent adverse events: Tabulation of all treatment-related adverse events

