 Tabulation of TEAE preferred terms per system organ class and per analysis period. Selecting only the thromboembolic TEAEs.

Population: safety population.

Table 14.3.1.15: Treatment-emergent adverse events: Tabulation of all hypersensitivity reactions

Tabulation of TEAE preferred terms per system organ class and per analysis period. Selecting only the hypersensitivity reactions.

Population: safety population.

Table 14.3.1.16: Treatment-emergent adverse events: Tabulation of all treatment-related hypersensitivity reactions

Tabulation of TEAE preferred terms per system organ class and per analysis period. Selecting only the hypersensitivity reactions that were treatment-related (as defined in Section 7.1.1).

Population: safety population.

Table 14.3.1.17: Treatment-emergent adverse events: Tabulation of all adverse events by subgroup

Tabulation of TEAE preferred terms per system organ class by subgroup. Following subgroups will be shown:

- Treatment extension (yes/ no)
- Baseline disease severity (very severe/ less severe)

Population: safety population.

Table 14.3.1.18: Treatment-emergent adverse events: Tabulation of all serious adverse events by subgroup

Tabulation of serious TEAE preferred terms per system organ class by subgroup. Following subgroups will be shown:

- Treatment extension (yes/ no)
- Baseline disease severity (very severe/ less severe)

Population: safety population.

Table 14.3.1.19: Treatment-emergent adverse events: Tabulation of all bleeding events by subgroup

Tabulation of bleeding event preferred terms per system organ class by subgroup. Following subgroups will be shown:

- Treatment extension (yes/ no)
- Baseline disease severity (very severe/ less severe)
- Antithrombotic agents (yes / no), this subgroup will be based on MedDRA coding (ATC term Antithrombotic Agents, ATC codes starting with B01A).

Population: safety population.

Table 14.3.1.20: Treatment-emergent adverse events: Tabulation of all thromboembolic events by subgroup.

Tabulation of TEAE preferred terms per system organ class and per analysis period (including number of events and incidence per 100 patient months) by subgroup. Following subgroups will be shown:

Refractory TTP (yes / no)

Population: safety population.

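### The adverse-event incidence per 100 patient months counts each subject once but keeps time after the first event in the denominator, so for common categories it falls as the period lengthens

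*SAP*

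**What the plan says.** SAP 7.1.2 plans a general adverse-event summary by treatment group and analysis period. It shows the number and percentage of subjects, the number of events, and an incidence per 100 patient months. The incidence is 100 times the number of subjects with the event, divided by "Total number of months observed within analysis period, summed for all subjects". Every row counts subjects with one or more events of the category. There are seven analysis periods, from the daily PE subperiod to the overall study period.

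The table index in SAP 14.6 repeats the measure. Table 14.3.1.1 lists "the number of events and the incidence per 100 patient months for the following" categories. Table 14.3.1.20, thromboembolic events by refractory TTP status, is specified as "including number of events and incidence per 100 patient months". Neither the index nor SAP 7.1 ends a subject's time at the first event.

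Two further provisions bear on observation time. Under SAP 4.3.6, for the Caplacizumab and Placebo columns "only data up to the switch are used in the analyses of these treatment groups". Table 14.1.1.5 summarizes period lengths: "The duration (days) is derived as follows: period end date – period start date + 1".

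**The concern.** Once a subject has had a first event, that subject cannot add to the numerator again in that row and period, but continues to add months to the denominator. For a rare category this hardly matters. For a category that most subjects meet, the figure tends towards 100 divided by mean follow-up in months, which describes the period length and not the drug.

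This is the only column in Table 14.3.1.1 that uses observation time, so a reader will take it as the adjustment for unequal observation. For bleeding and for any TEAE it does not do that job, and a figure for one period set against another partly reflects how long each period lasts.

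**Working it through.** The plan states no adverse-event rate, so there is no figure to reproduce. The check applies the SAP formula to a hazard that does not change.

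**Inputs.** Protocol 1.2.4 (Phase II): bleeding TEAEs 54.3% on caplacizumab and 37.8% on placebo; any TEAE 97.1% on caplacizumab; mean PE days 5.9 vs 7.9; exacerbation during treatment 8% vs 28%. The post-daily PE period is 30 days (Protocol 3.3). Assumptions: constant hazard, equal in the groups compared; Phase II percentages treated as risks over 7.9 + 30 = 37.9 days, because the documents do not give their window; PE days used as a proxy for the length of the daily PE subperiod.

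**Formula.** With daily hazard λ and period length T, the planned figure is proportional to (1 − exp(−λT))/T, which falls as T grows. Stopping time at the first event gives expected time at risk (1 − exp(−λT))/λ, so the rate is λ for every T.

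**Follow-up doubled.** If the risk over T is p, the ratio of new to old figure is [1 − (1 − p)²]/(2p) = 1 − p/2. The change is −5.0% at 10%, −18.9% at 37.8%, −27.1% at 54.3% and −48.5% at 97.1%.

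**Short against long period.** λ = −ln(1 − p)/37.9. Ratio = [(1 − exp(−7.9λ))/7.9] / (p/37.9).

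| Risk over 37.9 days | Risk over 7.9 days | 7.9-day figure ÷ 37.9-day figure |
|---|---|---|
| 10% | 2.2% | 1.04 |
| 37.8% | 9.4% | 1.20 |
| 54.3% | 15.1% | 1.33 |
| 97.1% | 52.2% | 2.58 |

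**Between arms, daily PE subperiod, 5.9 vs 7.9 days.** Fixed lengths: ratio = [(1 − exp(−5.9λ))/5.9] / [(1 − exp(−7.9λ))/7.9], giving 1.012, 1.020 and 1.087 at 37.8%, 54.3% and 97.1%. Exponentially distributed lengths, with q the 7.9-day risk in the table: λ = [q/(1 − q)]/7.9 and ratio = (1 + 7.9λ)/(1 + 5.9λ), giving 1.024, 1.040 and 1.152. So the ratio is about 1.01-1.04 for bleeding and 1.09-1.15 for any TEAE.

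**Between arms, whole double-blind period, columns stopped at the switch.** Caplacizumab: 92% observed 35.9 days and 8% observed 5.9 + s. Placebo: 72% observed 37.9 days and 28% observed 7.9 + s. The switch is assumed at s = 5 to 20 days after daily PE. Mean days are 33.9-35.1 vs 30.9-35.1. With the hazard set by the placebo-column risk, the caplacizumab/placebo ratio is 0.99-1.00 at 37.8% and 54.3%, and 0.93-1.00 at 97.1%. Adding 28 days of follow-up for non-switchers (overall study period) gives 0.98-0.99 and 0.87-0.92.

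**What the table already yields.** With n subjects, E events and incidence I in one row, total patient-months = 100 × n/I and the event rate = I × E/n, to rounding. The first-event rate needs time to first event, which is not tabulated; SAP 7.1.1 presents AE onset day in listings only.

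**The case against.** The measure is fully defined, nothing in the plan contradicts it, and no test or decision rule uses it. The subject counts, percentages and event counts stand beside it, and the recovery formulas above show that total patient-months and the event rate are implicit in the table. No section plans a comparison of the figure across analysis periods, some of which are nested. All of this stands, and it keeps the point minor. It does not make a once-per-subject numerator fit an all-time denominator.

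A reader might infer that the measure materially biases the comparison of arms. The documents do not support that. On Phase II exposure the protocol says: "The overall duration of exposure to study drug was similar in the two treatment arms". The double-blind ratios are close to 1 for bleeding. A reader might also put the Phase II bleeding percentage, or a risk near 90%, into the daily PE subperiod and obtain ratios of 1.06 to 1.30. Those risks are not consistent with the Phase II totals under a constant hazard: the 7.9-day risks are 9-15% for bleeding and 52% for any TEAE. Larger ratios need events concentrated early, and then a first-event rate helps less. With the hazard four times higher on days 1-2 of daily PE, the planned and first-event ratios are 1.16 vs 1.14 at 10% period risk and 1.18 vs 1.13 at 37.8%.

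**Conclusion.** The point holds as a minor one. For common rows the column depends on period length at an unchanged hazard: it drops by 19% to 49% when follow-up doubles, and it is 1.20 to 2.58 times higher in a 7.9-day than in a 37.9-day period, at risks of 37.8% to 97.1%. Rows at or below about 10% change by about 5% or less. The direction follows from the formula under a constant hazard; the sizes rest on the assumed 37.9-day window.

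Between arms the distortion is small for bleeding. It is noticeable only where nearly every subject has an event, and there the percentage itself already says little.

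Table 14.3.1.20 uses the same measure, and a reader might infer a distortion by refractory status. The documents give no period length by that status, so no size can be claimed for it.

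**What to change.** In SAP 7.1.2 and Tables 14.3.1.1 and 14.3.1.20, define the incidence as 100 × (subjects with at least one event of the category in the period) / (sum of months at risk).

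- Days at risk = min(date of first such event in the period, period end date) − period start date + 1, the inclusive count the SAP already uses. Months = days/30.4375, from the 365.25-day year in SAP 5.3.
- For the Caplacizumab Total column, start the clock at the first caplacizumab dose, which is the first open-label dose for subjects who switch from placebo.
- Print patient-months per row, since the denominator now differs by row.
- State one rule for incomplete AE start dates: for example, the earliest date consistent with the known parts and the allocated period, with the number of subjects affected in a footnote.

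Alternatively or in addition, report 100 × (number of events)/(total months), labelled as an event rate. This uses counts already tabulated and needs no new date rule.

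The cost is one formula in the SAP and the AE program, using dates already collected. There are three downsides to state:

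- SAP 7.1.1 says of AE dates: "There will be no imputation of other missing date(time) fields". The partial-date rule is therefore an addition, and the earliest-date version slightly raises the rate.
- In short periods with high risk the rate depends on the day-count convention. Over 8 days with a constant daily hazard, it is 761 per 100 patient-months if the event day is counted and 1015 if it is not, at 90% risk; at 37.8% it is 175 vs 186.
- If the hazard is not constant, the fix reduces the dependence on follow-up but does not remove it. With a hazard four times higher in the first 7 of 37 days and follow-up doubled, the planned figure falls 33% and the first-event rate 16% at 54.3% risk; at 97.1% the falls are 49% and 4%.
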